c. Justification and safety information if non-FDA approved drugs without an IND will be administered.

N/A

7. Study Statistics

- a. Primary outcome variable.
 - Anti-HPV16 antibody titers measured four weeks after the second dose.

b. Secondary outcome variables.

- Antibody titers to the other 8 HPV types
- Seropositivity for each HPV type after 1-dose and 2-doses
- Percentage of participants who complete 1-dose, 2-dose, or 3-dose vaccination
- Percentage of participants with baseline titers suggestive of natural infection or prior vaccination
- Characteristics and percentage of participants who completed study visits in-person using their own transportation, required Lyft, or requested a home-visit. Characteristics will include individual demographic characteristics, sexual reproductive health history, STI history, neighborhood median income based on zipcode and neigborhood deprivation index based on address.
- Thematic coding of field notes if home visits were conducted

c. Statistical plan including sample size justification and interim data analysis.

Geometric mean titer (GMT) ratios for each HPV genotype will be compared between the 2dose and 3-dose regimen. As a non-inferiority trial, the primary analysis will use the perprotocol analysis. One-sided 90% confidence intervals (adjusted for multiple comparisons) will be constructed for the primary immunogenicity, which is the accepted method of reporting noninferiority results. Antibody GMTs at month-7 (4 weeks after 2nd dose) among participants who received the 2-dose regimen will be compared with historical controls who received the 3-dose regimen.²⁴ The criteria for declaring non-inferiority will be defined as the lower bounds of the multiplicity-adjusted 90% CI for the ratio of antibody GMT greater than 0.67. This noninferiority margin was selected based on bridging studies used for licensure.²⁵

Table 1: Statistical Intervals²⁶

Confidence	Sample	Actual Distance	Standard
Level	Size (N)	from Mean to Limit	Deviation (S)

0.900	107	0.125	1.000
0.900	107	0.150	1.200

Estimating the standard deviation of the GMT ratio to be 1.2 based on preliminary data, a sample size of 107 will produce a one-sided 90% confidence limit with a distance from the mean to the limit of 0.15. That is, if the GMT mean ratio is \geq 0.82, we will be 90% confident that the true ratio is not less than 0.67. To allow for almost 28% attrition, we will enroll 231 subjects.

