Secondary endpoints include % seropositive at baseline (before administration of 1st dose), % of participants who seroconverted. Descriptive statistics will be performed. Additionally, we will determine if hormone levels are associated with seropositivity and GMTs.

Given the success of our home visits as a method to increase retention, we would like to write a separate paper (brief report) to share our methodology with other researchers.

De-identified serum samples will be shipped to a Merck designated laboratory to perform the proprietary assay for HPV antibodies. No PHI will be shipped. Shipment will occur at study end in one batch. Hormone levels will be shipped to OHSU for analyses.

d. Early stopping rules.

Participants will be temporarily or permanently removed from the study regarding a severe AE related to the vaccination. Any participants with a positive pregnancy test after the baseline visit will be permanently removed from the study.

Participants may voluntarily withdraw from the study for any reason at any time. The PI may withdraw participants before their scheduled termination visit in order to protect their safety, and/or if participants are unable or unwilling to comply with study procedures. During the study, any abnormalities identified by history, physical examination, or laboratory tests will be reassessed until resolution, an explanation is found, or up until one month if changes are deemed permanent.

8. Risks

a. **Medical risks, listing all procedures, their major and minor risks and expected frequency.** Risks of the proposed study include the risk of pain, infection, dizziness, swelling, bruising, or bleeding from the needle stick that can occur with phlebotomy. Risks commonly associated with venipuncture include bleeding, occasional bruising at the site of venipuncture, hematoma, or infection. Rare complications (1/100) include lightheadedness or fainting. Other risks include infection, damage to the vein, blood clot or stroke, if a large amount of air enter the vein, but these are rare. Early pregnancies may not be detected even with a known last menstrual period and urine pregnancy test. The vaccine is not a live virus and does not cause birth defects. Administration of the vaccine may cause injection site pain, injection site swelling, redness of the skin, allergic reactions, and/or headaches. The vaccine also has a small risk of syncope.

b. Steps taken to minimize the risks.

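### Section 7c's 90% assurance at a GMT ratio of 0.82 does not follow from its own calculation, which also omits control variance and the multiplicity adjustment that the criterion requires

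*Combined protocol and SAP*

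**What the plan says.** All of the following is in section 7 (Study Statistics) of the combined protocol and SAP.

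- **7a, primary outcome:** "Anti-HPV16 antibody titers measured four weeks after the second dose". No other type is listed.
- **7b, secondary outcomes:** these include "Antibody titers to the other 8 HPV types".
- **7c, comparison:** GMT ratios are compared for every genotype. The month-7 GMTs "will be compared with historical controls who received the 3-dose regimen". The intervals for the primary immunogenicity analysis are one-sided 90%, adjusted for multiple comparisons. Neither the family nor the method is named.
- **7c, criterion:** the lower bound of the "multiplicity-adjusted 90% CI for the ratio of antibody GMT greater than 0.67".
- **7c, sizing:** "Estimating the standard deviation of the GMT ratio to be 1.2 based on preliminary data", N = 107 gives a distance of 0.15 from the mean to the one-sided 90% limit. From this the plan concludes that at an observed ratio of 0.82 or more "we will be 90% confident that the true ratio is not less than 0.67".
- **7c, enrolment:** "To allow for almost 28% attrition, we will enroll 231 subjects".

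The documents give no log base for the 1.2, no size or SD for the control group, and no formula for the final confidence limit.

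**The concern.** The sizing sentence describes a different calculation from the one that will decide the trial. It differs in three ways.

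1. **Scale.** The distance is taken off the ratio by subtraction, whereas a GMT ratio is analysed on the log scale.
2. **Control group.** The formula has one sample, yet the ratio has a historical control GMT in its denominator.
3. **Level.** The distance is unadjusted, while the criterion in the same section uses an adjusted limit. If HPV16 alone decides, as 7a suggests, no adjustment is needed and the sizing level is right. If several types are covered, as 7c may intend, it is not.

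The third choice can decide whether an observed 0.82 passes. Section 7c is also the only description of the final interval. If the log base, the treatment of control variance and the family stay open until results are known, the conclusion could depend on choices made after seeing the data.

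**Working it through.** **Inputs from section 7c:** N = 107, SD = 1.2, one-sided 90%, margin 0.67, illustrative ratio 0.82, 231 enrolled, 28% attrition.

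**Assumptions, not in the documents:** the log base; a control SD of 1.2 (ln) and control numbers of 127, 128 and 1000; Bonferroni as the adjustment method.

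**Step 1. Reproduce the plan's figure.** Distance = t(0.90, 106) × 1.2/√107 = 1.2896 × 0.1160 = 0.1496, which is the plan's 0.15. The smallest N giving 0.15 or less is 107. Then 0.82 − 0.15 = 0.67. So the formula is one-sample, unadjusted, and subtracted on the ratio scale.

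**Step 2. Put the distance on the log scale (fixed controls, no adjustment, N = 107).**

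- *Natural log:* the limit at 0.82 is 0.82 × exp(−0.1496) = 0.706. The ratio needed is 0.67 × exp(0.1496) = 0.778. Confidence at 0.82: ln(0.82/0.67) = 0.2020; 0.2020/0.1160 = 1.741; T(106 df) gives 95.8%.
- *log10:* the limit is 0.82 × 10^(−0.1496) = 0.581. The ratio needed is 0.67 × 10^0.1496 = 0.946. Confidence: log10(0.82/0.67) = 0.0877; 0.0877/0.1160 = 0.756; 77.4%. This is an extreme reading, because 10^1.2 is about a 16-fold change per SD.

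**Step 3. Add control sampling error (ln, equal SD, no adjustment, N = 107).** SE = 1.2 × √(1/107 + 1/m), with m controls and m + 105 degrees of freedom.

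- m = 127: SE = 0.1575, confidence at 0.82 = 89.96%
- m = 128: SE = 0.1572, confidence = 90.00%
- m = 1000: SE = 0.1221, confidence = 95.1%

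On these assumptions 0.82 gives less than 90% only with fewer than about 128 controls.

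**Step 4. Add the adjustment (ln).** Ratio needed = 0.67 × exp[t(1 − 0.10/k) × SE], where k is the number of types in the family. The 166 evaluable is 231 × 0.72 = 166.3.

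| Types adjusted for | Controls | N = 107 | N = 166 |
|---|---|---|---|
| k = 1 | fixed | 0.778 | 0.755 |
| k = 1 | 1000 | 0.784 | 0.762 |
| k = 9 | fixed | 0.877 | 0.831 |
| k = 9 | 1000 | 0.886 | 0.843 |

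For example, k = 9, fixed controls, N = 107: t(1 − 0.10/9, 106) = 2.3206; 2.3206 × 0.1160 = 0.2692; 0.67 × exp(0.2692) = 0.877.

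**Step 5. Which N applies.** The enrolment sentence does not lead back to 107: 107/0.72 = 149, not 231. The per-protocol number may differ from both 107 and 166, so both are shown.

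**The case against.** **The slip may favour caution.** This stands. With an ln SD, fixed controls and HPV16 alone, the plan understates its assurance. A reader might infer from the arithmetic error that the trial is too small or that the claim is inflated. The documents do not support that, because the direction depends on inputs they do not give.

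**The 90% might be right by coincidence.** This also stands. A reader might infer that 90% is wrong under any log-scale analysis. That holds only with controls treated as fixed; about 128 controls with an equal ln SD would give 90.0% at 0.82. The plan did not make that calculation, so the figure is unsupported rather than shown to be false in every case.

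**Subtraction would be coherent for an arithmetic mean of individual titers, each divided by a fixed control value.** True, and 7c's wording for the ratio is loose enough to suggest it. But that is not a GMT analysis, which is what the criterion specifies.

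**Sections 7a and 7c do not state two conflicting counts.** Correct: 7c gives no count. The defect is an undefined family beside a single primary type, and the results for nine types are conditional on that reading.

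**The 0.82 is only a planning illustration in a pilot.** Pass or fail will be set by the observed lower bound. That limits the harm, but the trial still has a formal rule for declaring non-inferiority, and the formula for that bound is missing.

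**Conclusion.** The concern holds in this form: the 90% statement at 0.82 does not follow from the plan's calculation, and the sizing does not describe the criterion to be applied.

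With fixed controls, no adjustment, N = 107 and an ln SD of 1.2, the limit at 0.82 is 0.706, confidence is about 96% and 0.778 would suffice. A log10 SD would give about 77% and 0.946. Control variance matters mainly if the control group is small. The undefined adjustment matters most: with nine types under Bonferroni and an ln SD, 0.82 fails at both 107 and 166 evaluable, with fixed controls or with 1000. If HPV16 alone decides, that part falls away.

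A reader might infer that 0.82 would fail in this trial. The documents do not establish that, since it needs either a multi-type family, a small control group or a log10 SD, and none of these is stated.

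This should be corrected. It does not by itself show that enrolment is inadequate.

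**What to change.** 1. State what the 1.2 is (SD of individual log titer, or something else) and its log base.
2. Reconcile 7a and 7c. If HPV16 alone decides non-inferiority, drop the adjustment from the primary criterion. If claims are made for several types, name the family and the method.
3. For both sizing and final analysis, define the lower limit as the back-transform of [difference in mean log titer − t × √(SD₁²/n(2-dose) + SD₀²/n(control))], with t at the level chosen in item 2.
4. Replace the 0.82 and 90% sentence with the ratio this gives for the expected evaluable N and the actual control N and SD, and reconcile 107, 28% and 231.

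Record this before the HPV antibody results are seen, if they have not yet been produced. Section 7c plans that "Shipment will occur at study end in one batch", which makes this possible, but the documents do not show whether the batch has already been assayed.

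The cost is a few sentences in 7a and 7c. The control N and SD can be requested with the historical data that section 12 says the sponsor's laboratory provides. Visits, samples and enrolment do not change. The downside is that the restated ratio may be less favourable than 0.82, for example 0.831 at 166 evaluable with nine types and fixed controls. With HPV16 alone, an ln SD and a large control group it would be more favourable.

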vaccination. Prior studies demonstrate <15% of pregnant women received any doses of HPV vaccine and <8% completed the series.¹⁵⁻¹⁸ Given this window of opportunity, a few investigators have implemented postpartum HPV vaccination at their institutions, and the Departments of Health in the states of New York and Washington recommend it for women who have not completed the series.^{18,19} One of the first postpartum HPV vaccination studies enrolled a sample of 150 Hispanic women who tolerated the vaccination with few side effects and patients reported a high degree of satisfaction.²⁰ However, 30% of the women completed all 3 doses, 23% received two doses, and 41% received only one dose during hospitalization. Completion of the series of three HPV doses was a challenge. The second study, also done in Texas, used patient navigators who used multiple reminder methods (texting, mailed reminders, and phone calls) to increase completion rates. This study reported a 65% completion rate and 75% of postpartum women received at least one dose.²¹ Future studies should determine the optimal method to ensure vaccine series completion while using minimal resources and existing staffing.

Two Dose Regimen for HPV Vaccination

A two-dose regimen includes administration of an inactivated vaccine with the first dose as the priming dose and the second distant dose resulting in consolidation of the immune response.²² The second dose administered at 6-months to allow complete initial B cell response stimulation; affinity-matured B cells produce an amnestic response after booster, but affinity maturation takes at least four months to develop. Recent studies have demonstrated non-inferiority of HPV vaccination in a two-dose regimen in adolescents.²² A two-dose regimen may be beneficial in older patients as well, especially those who have difficulty with follow up for multiple doses of a vaccine regimen, but this has not been studied.

4. Study Procedures

a. Study design, including the sequence and timing of study procedures Pilot, non-inferiority clinical trial using historical controls

Participants will have whole blood drawn at 0-months, 6- to 12-months, and one month after the second dose of the vaccine. The HPV vaccine will be administered at 0-months, 6- to 12-months, and two to five months after the second dose of the vaccine. Each blood draw will consist of 15 mL to measure HPV serologies and hormone levels.

Initial contact

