- **c.** Study duration and number of study visits required of research participants. Study duration is two years. Each participant will undergo four study visits over 12 months on average. Two of the study visits can occur during routine clinical care.
- **d.** Blinding, including justification for blinding or not blinding the trial, if applicable. This is an open-label non-inferiority clinical trial and historical controls will be used.
- e. Justification of why participants will not receive routine care or will have current therapy stopped.

N/A

- **f.** Justification for inclusion of a placebo or non-treatment group. This is a pilot, open-label non-inferiority clinical trial and historical controls will be used.
- g. Definition of treatment failure or participant removal criteria.

Participants who suffer severe adverse events from the HPV vaccine or who become pregnant will be withdrawn from the study.

h. Description of what happens to participants receiving therapy when study ends or if a participant's participation in the study ends prematurely.

Participants will resume routine clinical care.

i. If biological materials are involved, please describe all the experimental procedures and analyses in which they will be used.

The study site will adhere to standards of good laboratory practice and local standard operating procedures for proper collection, processing, labeling, transport, and storage of specimens to the local laboratory and outside laboratories

JHH or Bayview Clinical Laboratory or ObGyn clinic

- POC Urine hCG Test (Pregnancy Test)
- Estrogen and Progesterone levels

JHU Research Laboratory

• Whole blood processing for serum and storage at -80°C.

Specimens will be labeled with a unique study identifier (study number) instead of personal identifiers. Blood samples will be stored at a JHU research laboratory at -80° C and shipped to a designed Merck laboratory at the end of the study.

Merck Laboratory

Serum will be tested for vaccine HPV type antibodies by competitive Luminex immunoassay (cLIA). A participant will be defined as anti-HPV 6/11/16/18/31/33/45/52/58 positive if her anti-HPV serum level is ≥30, ≥16, ≥20, ≥24, ≥10, ≥8, ≥8, ≥8, or ≥8 milli Merck units (mMU)/mL for the 9 types, respectively. Assays to be performed by Merck's designee.

5. Inclusion/Exclusion Criteria

Inclusion Criteria

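### The enrolment target of 231 does not follow from 107 evaluable participants and almost 28% attrition: those inputs give about 149, and 231 with 28% loss leaves about 166.

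*Combined protocol and SAP*

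**What the plan says.** The sample size is justified in Section 7c (statistical plan). Taking a standard deviation of 1.2, the plan says that "a sample size of 107 will produce a one-sided 90% confidence limit with a distance from the mean to the limit of 0.15". Table 1 in the same section shows the same result: N = 107 at the 90% level, with a distance of 0.150 for a standard deviation of 1.2 and 0.125 for 1.0. The paragraph ends: "To allow for almost 28% attrition, we will enroll 231 subjects".

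107 is the only evaluable number given, and almost 28% is the only loss rate. The same section makes the per-protocol analysis primary. On design, Section 4d says: "This is an open-label non-inferiority clinical trial and historical controls will be used".

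The documents give some other information on retention. Section 3 (Postpartum HPV Vaccine Studies) reports that in one earlier programme "30% of the women completed all 3 doses, 23% received two doses, and 41% received only one dose during hospitalization". Of a second programme it says: "This study reported a 65% completion rate and 75% of postpartum women received at least one dose". Section 7c also refers to the trial's own experience: "Given the success of our home visits as a method to increase retention".

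**The concern.** The last sentence of the justification presents 231 as what results when almost 28% attrition is added to 107. It is not that result, and the difference is far larger than rounding.

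This paragraph is the only basis given for the number of women enrolled. As it stands, it supports two readings. If 28% is the expected loss, about 166 women should be evaluable and the precision statement built on 107 understates what the trial would deliver. If 107 is the expected evaluable number, the plan anticipates losing more than half of those enrolled while reporting little more than a quarter. The second reading would matter for interpretation, because a per-protocol set that retains under half of participants, compared with an external historical group, raises an obvious question of selection.

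**Working it through.** **Inputs, all from Section 7c except the last**

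- Evaluable N: 107
- One-sided 90% limit, standard deviation 1.2, distance 0.15
- Attrition: almost 28% (27% to 28% tried)
- Enrolment target: 231
- One enrolled group against historical controls (Section 4d)

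**Step 1. Reproduce 107.** Distance = t(0.90, N−1) × SD / √N.

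- N = 107, SD 1.2: 0.1496, which rounds to the stated 0.150
- N = 107, SD 1.0: 0.1247, which rounds to the stated 0.125
- The smallest N meeting either target is 107 (106 with the normal quantile)

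So 107 is sound on the plan's own formula. The break comes in the step from 107 to 231.

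**Step 2. Inflate 107 for attrition.** Enrolment = N / (1 − d).

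| Attrition d | 107/(1 − d) | Enrol |
|---|---|---|
| 27% | 146.6 | 147 |
| 27.5% | 147.6 | 148 |
| 28% | 148.6 | 149 |

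Enrolling 148 and keeping 107 is a loss of 1 − 107/148 = 27.7%, which fits the plan's wording of almost 28%. The common mistaken inflation, 107 × 1.28 = 137, does not give 231 either.

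**Step 3. Work back from 231.**

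- With 28% loss: 231 × 0.72 = 166.3, so about 166 evaluable and 65 lost
- If 107 remain: 231 − 107 = 124 lost, and 1 − 107/231 = 53.7%
- Excess over 149: 231 − 149 = 82, and 231/149 = 1.55

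**Step 4. Try other routes to 231.**

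| Route | Result |
|---|---|
| 28% applied twice, 107/0.72² | about 207 |
| 28% applied three times, 107/0.72³ | about 287 |
| Two-sided 90% interval, 173.2/0.72 | about 241 |
| Two arms of 107, 214/0.72 (not this design) | about 298 |
| First postpartum study, 30% + 23% = 53% with two or more doses, 107/0.53 | about 202 |
| Second postpartum study, 65% completion, 107/0.65 | about 165 |

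None gives 231.

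**Step 5. Effect on stated precision.** At N = 166 and SD 1.2 the Step 1 formula gives 0.1198, about 0.12 instead of 0.15. On the plan's own additive reading, its threshold of 0.82 (0.67 + 0.15) would become 0.67 + 0.12 = 0.79. This takes the formula at face value. It includes no multiplicity adjustment and no variance for the historical controls, and it leaves open whether these quantities belong on the ratio or the log scale.

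**The case against.** The arithmetic itself is not disputable; the case on the other side concerns its weight and its possible explanations.

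- **The error is conservative.** 231 exceeds the 149 that the stated inputs need, and the endpoint, margin, analysis set and decision rule do not depend on it. This stands, and it limits the severity. It does not make the sentence correct.
- **The plan does name 107 as the number that gives the planned precision.** True, but it does not say whether 107 is the expected number or a minimum well below it.
- **Other losses may lie behind 231.** Consent can be taken before delivery (Section 4a), stillbirth is an exclusion (Section 5), and a later positive pregnancy test leads to withdrawal (Sections 4a, 4g and 7d). The authors may not have counted these as attrition. The plan attaches no rate to any of them, so they cannot reconcile the figures as written.
- **Combined rates come nearer.** 107/(0.75 × 0.65) = 219 and 107/(0.72 × 0.65) = 229. The plan states neither product, and the second may count the same losses twice. It also amounts to 1 − 0.72 × 0.65 = 53% total loss, which is not what the sentence says. The 65% is a completion rate for the full series, whereas the primary endpoint needs the second dose and the blood draw at Visit 3.
- **The 0.79 figure depends on scale.** If 0.15 and 0.12 were natural-log distances, the thresholds would be 0.67 × exp(0.15) = 0.78 and 0.67 × exp(0.12) = 0.76. This is fair. The figure is only an illustration on the plan's own terms, and the finding does not rest on it.

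**Conclusion.** The concern holds. The evaluable number, attrition rate and enrolment target in Section 7c cannot all be right together. Taking 107 and 28% as given, the target should be about 149, not 231. Taking 231 and 28%, the evaluable number is about 166, not 107. Taking 231 and 107, the loss is 53.7%, not 28%.

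This rests only on the plan's stated figures and on there being one enrolled group. It does not show the trial to be undersized. Nor do the documents show which figure is wrong. That 148 enrolled gives a 27.7% loss suggests that 231 may have been changed without updating the attrition wording, but that is inference. It is a definite inconsistency in a core design figure, should be fixed, and is cheap to fix.

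**What to change.** Rewrite the sentence so that the three figures agree, and state which one was in error. There are three ways to do it:

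- **(a) Keep 231 and 107.** State that 231 allows for about 54% total loss, and break that loss down. For example, 28% attrition followed by about 36% per-protocol exclusions (1 − 107/166 = 35.5%) would reach 107, but the plan currently states no such allowance. Losses between consent and first vaccination, and withdrawals for pregnancy, belong in this breakdown.
- **(b) Keep 231 and 28%.** State that about 166 are expected to be evaluable, and recompute the distance (about 0.12 by the Table 1 formula at SD 1.2), after confirming the scale on which SD and distance are expressed.
- **(c) Keep 107 and 28%.** Correct the target to about 149.

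Options (a) and (b) need protocol wording only. Option (c) also lowers the stated enrolment target by 82. It loses nothing against the stated 107, but it would reduce precision for secondary outcomes measured on all enrolled women, such as dose completion and baseline titers. Section 7c speaks of home visits as already successful, so enrolment so far should be checked before choosing (c).
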